6.1.1.2. Active Treatment Period – Month 3 to Month 96 Visits

For subjects in the active treatment period, study visits will be scheduled at the study site at Months 3, 6, 9, 12, 15, 18, 21, 24, 27, 30, 33, 36, 39, 42, 45, 48, 51, 54, 57, 60, 63, 66, 69, 72, 75, 78, 81, 84, 87, 90, 93, and 96 (within ± 14 days of the projected visit date based on the actual baseline visit date).

The following safety and efficacy evaluations will be performed at all visits during the active treatment period unless otherwise indicated:

1. Collect/update contact information, including primary care physician or other treating physician.
2. Concomitant medications (DMARDs, corticosteroids, NSAIDs, and anti-infective agents) and non-drug treatments received due to an adverse event.
3. Physical examination (performed by a physician at months 12, 24, 36, 48, 60, 72, 84, and 96 only).
 - The physical examination will include completion of the Tanner Assessment for subjects < 18 years or who have a score of < 5 on 1 or more applicable domain(s).
4. Vital signs: Temperature, blood pressure (mmHg) and pulse rate (beats/min, after sitting for at least 5 minutes).
5. Height (cm, at months 12, 24, 36, 48, 60, 72, 84, and 96 only).
6. Weight (kg):
 - For subjects who are < 18 years of age and who weigh ≤ 62 kg (at all visits).
 - For subjects who are ≥ 18 years of age or weigh > 62 kg (at months 12, 24, 36, 48, 60, 72, 84, and 96 only).
7. Laboratory evaluations (ie, hematology, blood chemistry, and CRP, at months 6, 12, 18, 24, 30, 36, 42, 48, 54, 60, 66, 72, 78, 84, 90, and 96 only). Additional testing may be performed according to local guidelines or standard of care and for follow-up of abnormal laboratory test results.
8. For female subjects, evaluate childbearing potential. The evaluation must be documented in the subject's source documents.
9. Female subjects who, in the opinion of the investigator, are of childbearing potential will have a urine pregnancy test at each visit; this includes subjects who are

- menstruating at the time of the visit. For these subjects, a negative test result must be available before dispensing and/or administration of investigational product. Pregnancy tests will also be done whenever one menstrual cycle is missed during the active treatment period or when potential pregnancy is otherwise suspected. Pregnancy tests may also be repeated as per request of IRB/IECs or if required by local regulations.

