6.1.2.2. Withdrawal Period

Subjects who are eligible and consent to participate in the withdrawal period will have the following visits conducted:

- Subjects who enter directly into the withdrawal period will have the first post baseline visit conducted at the study site 1 month (± 7 days) after the baseline visit.
- Subjects who participated in the active treatment period of study B1801023 will have the first withdrawal visit conducted at the study site 1 month (± 7 days) after the active treatment early withdrawal visit.
- Subsequent visits will occur at the study site every 3 months after the baseline or active treatment early withdrawal visit for up to a year and then every 6 months thereafter. Subsequent visits must be scheduled within ± 14 days of the projected visit date based on the actual date of the baseline or active treatment period early

withdrawal visit. Subjects who do not experience disease relapse will continue in the withdrawal period for a total of 96 months from the time of the baseline visit in study B1801023.

The following assessments will be performed at all visits during the withdrawal period unless otherwise indicated:

1. Ensure that the subject meets inclusion/exclusion criteria that apply to the withdrawal period.
2. Those subjects who do not meet entry criteria for the withdrawal period will be asked to participate in the observational period.
3. Ensure the most recent version(s) of the informed consent/assent for withdrawal/re-treatment period has been signed and dated.
4. Collect/update contact information, including primary care physician or other treating physician.
5. Concomitant medications (DMARDs, corticosteroids, NSAIDs, and anti-infective agents) and non-drug treatments received due to an adverse event.
6. Physical examination (performed by a physician and conducted at months 12, 24, 36, 48, 60, 72, 84, and 96 only).
 - The physical examination will include completion of the Tanner Assessment for subjects <18 years or who have a score of <5 on 1 or more applicable domain(s).
7. Vital signs: Temperature, blood pressure (mmHg) and pulse rate (beats/min, after sitting for at least 5 minutes).
8. Height (cm, at months 12, 24, 36, 48, 60, 72, 84, and 96 only).
9. Weight (kg):
 - For subjects who are <18 years of age and who weigh ≤ 62 kg (at all visits).
 - For subjects who are ≥ 18 years of age or weigh > 62 kg (at months 12, 24, 36, 48, 60, 72, 84, and 96 only).

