6.1.2.3. Re-Treatment Period

Subjects who are eligible for re-treatment with investigational product will have study visits conducted at the study site every 3 months after the re-treatment assessment visit. Visits must be scheduled within ± 14 days of the projected visit date based on the actual date of the re-treatment assessment visit. Subjects who remain eligible for re-treatment will continue in

the re-treatment period for a total of 96 months (± 14 days) from the time of the baseline visit in study B1801023.

The following assessments will be performed at all visits during the re-treatment period:

1. Ensure that the subject meets the inclusion/exclusion criteria that apply to the re-treatment period.
2. Those subjects who do not meet entry criteria for the re-treatment period will be asked to participate in the observational period.
3. Ensure the most recent version(s) of the informed consent/assent for withdrawal/re-treatment period has been signed and dated.
4. Collect/update contact information, including primary care physician or other treating physician.
5. Concomitant medications (DMARDs, corticosteroids, NSAIDs, and anti-infective agents) and non-drug treatments received due to an adverse event.
6. Physical examination (performed by a physician and conducted at months 12, 24, 36, 48, 60, 72, 84, and 96 months only).
 - The physical examination will include completion of the Tanner Assessment for subjects <18 years or who have a score of <5 on 1 or more applicable domain(s).
7. Vital signs: Temperature, blood pressure (mmHg) and pulse rate (beats/min, after sitting for at least 5 minutes).
8. Height (cm, at months 12, 24, 36, 48, 60, 72, 84, and 96 only).
9. Weight (kg):
 - For subjects who are <18 years of age and who weigh ≤ 62 kg (at all visits).
 - For subjects who are ≥ 18 years of age or weigh > 62 kg (at months 12, 24, 36, 48, 60, 72, 84, and 96 only).
10. Laboratory evaluations (ie, hematology, blood chemistry, and CRP) at months 3, 6, 9, 12, and every 6 months thereafter.
11. For female subjects, evaluate childbearing potential. The evaluation must be documented in the subject's source documents.
12. Female subjects who, in the opinion of the investigator, are of childbearing potential will have a urine pregnancy test; this includes subjects who are menstruating at the time of the visit. Pregnancy tests will also be done whenever one menstrual cycle is

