5.7. Laboratory, Vital Signs, Tanner Stage Assessment

For laboratory data, vital sign measurements and other continuous safety data, the number of observations, mean, standard deviation, median, minimum, maximum will be summarized by visit. Height, weight, BMI, and Tanner scores will be summarized using the number of observations, mean, standard deviation, median, minimum, and maximum by age group (ages 2-4, 5-11 and 12-17 years at start of parent study). The visits shown in these reports will be the baseline visit from the parent study, weeks 12, 24, 48, and 96, from the parent study and all visits from the extension study where

the data is collected. Some additional analyses of the Tanner data that takes age at time of measurement into account may also be done.

The Potentially Clinically Important (PCI) Flag is a derived flag value based on the PCI criteria defined for laboratory data captured in the study. The PCI criteria are based on NCI toxicity criteria. The number (%) of subjects with PCI events will also be provided for the lab data.

These summaries will be performed for FAS (active period (both parent and extension studies)), WAS, and RTAS.

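### The percentages of subjects with a potentially clinically important (PCI) laboratory result are not comparable between the active, withdrawal and re-treatment periods, because observation length and first-year testing density both differ.

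*SAP*

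**What the plan says.** SAP 5.7 derives a PCI flag for laboratory values from toxicity criteria and then states: "The number (%) of subjects with PCI events will also be provided for the lab data". The analysis sets follow: "These summaries will be performed for FAS (active period (both parent and extension studies)), WAS, and RTAS". The active-period figure therefore pools both studies. SAP 1 describes the combined data as covering up to 10 years. For PCI results, SAP 5.7 gives no per-test denominator, no common set of visits and no adjustment for time. Its by-visit wording is attached to the continuous summaries.

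The protocol sets three laboratory schedules:

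- **Extension active period** (Protocol 6.1.1.2): "Laboratory evaluations (ie, hematology, blood chemistry, and CRP, at months 6, 12, 18, 24" and on at 6-month steps to Month 96.
- **Withdrawal period** (Protocol 6.1.2.2): subjects coming from active treatment have the "first withdrawal visit conducted at the study site 1 month" after leaving it, and direct entrants have theirs 1 month after baseline. Later visits are "every 3 months after the baseline or active treatment early withdrawal visit for up to a year and then every 6 months thereafter". The list of procedures opens with "The following assessments will be performed at all visits during the withdrawal period unless otherwise indicated", and its laboratory item carries no month restriction.
- **Re-treatment period** (Protocol 6.1.2.3): "Laboratory evaluations (ie, hematology, blood chemistry, and CRP) at months 3, 6, 9, 12, and every 6 months thereafter".

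Protocol 9.4.2 plans, for PCI laboratory measurements, a frequency, a percentage and a rate per 100 subject-years of etanercept exposure. SAP 5.7 keeps the first two and does not carry over the rate.

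**The concern.** A subject counts once in the PCI percentage if any test is flagged. At the same underlying risk, a subject tested more often, or followed longer, is more likely to be counted. The three periods differ on both, and nothing in SAP 5.7 removes either difference.

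Readers will set the three columns side by side, because they appear to show laboratory safety on continuous etanercept, off it, and after restarting it. For cytopenias or transaminase rises, a gap between columns could be a drug effect, a result of how long subjects stayed in the period, or a result of how often blood was drawn. The planned table gives no means of telling these apart.

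**Working it through.** The documents give no PCI rate, so there is no planned figure to reproduce. The draw counts come from the documents. The per-test probability p is an assumption, equal in all periods and independent between tests.

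**Step 1. Scheduled post-baseline draws per subject.** Counted from Protocol 6.1.1.2, 6.1.2.2 and 6.1.2.3 and the Schedules of Activities. Baseline, early-withdrawal, re-treatment-assessment and unscheduled draws are left out.

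| Time in period | Extension active | Withdrawal | Re-treatment |
|---|---|---|---|
| First 12 months | 2 (Months 6, 12) | 5 (Months 1, 3, 6, 9, 12) | 4 (Months 3, 6, 9, 12) |
| Months 13 to 24 | 2 | 2 | 2 |
| Total to 24 months | 4 | 7 | 6 |
| Total to 96 months | 16 | 19 | 18 |

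The density difference lies entirely in the first 12 months.

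**Step 2. Density effect at equal follow-up.** P(at least one PCI result) = 1 − (1 − p)^k. At 12 months k = 2, 5, 4. With p = 2%: 1 − 0.98² = 4.0%; 1 − 0.98⁵ = 9.6%; 1 − 0.98⁴ = 7.8%.

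| p | Active | Withdrawal | Re-treatment |
|---|---|---|---|
| 0.5% | 1.0% | 2.5% | 2.0% |
| 1% | 2.0% | 4.9% | 3.9% |
| 2% | 4.0% | 9.6% | 7.8% |
| 5% | 9.8% | 22.6% | 18.5% |

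At p = 2% the withdrawal-to-active ratio is 2.4 at 12 months. By 96 months the figures are 27.6%, 31.9% and 30.5%, and the ratio is about 1.15.

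**Step 3. Length effect in the sets actually planned.** SAP 5.7 lists four post-baseline parent visits for display (weeks 12, 24, 48, 96). Added to 16 extension draws, a full active course has at least 4 + 16 = 20. A subject who leaves withdrawal at 6 months has 3 (Months 1, 3, 6). A 6-month stay is plausible: the background in Protocol 1.2 cites a 50% probability of being symptom-free at 6 months off etanercept.

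| p | 20 draws, full active course | 3 draws, 6-month withdrawal |
|---|---|---|
| 0.5% | 9.5% | 1.5% |
| 1% | 18.2% | 3.0% |
| 2% | 33.2% | 5.9% |
| 5% | 64.2% | 14.3% |

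This runs opposite to Step 2, at the same risk per test.

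**Step 4. Dependence on duration.** Take one abnormality with onset uniform over 12 months and lasting d months. The chance that a scheduled draw falls within it is Σ min(gap between draws, d) / 12. The gaps are 6, 6 (active); 1, 2, 3, 3, 3 (withdrawal); 3, 3, 3, 3 (re-treatment).

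| d | Active | Withdrawal | Re-treatment |
|---|---|---|---|
| 1 month | 2/12 = 17% | 5/12 = 42% | 4/12 = 33% |
| 2 months | 4/12 = 33% | 9/12 = 75% | 8/12 = 67% |
| 3 months | 6/12 = 50% | 12/12 = 100% | 12/12 = 100% |
| 6 months | 100% | 100% | 100% |

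An abnormality lasting 6 months or more is caught under every schedule.

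**Step 5. Would the Protocol 9.4.2 rate repair it?** Dividing by subject-years addresses length but not density: in year 1 the tests per subject-year are still 2, 5 and 4. Its denominator is etanercept exposure, to which time off the drug contributes nothing.

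**Step 6. Does the fix work?** Under the same model, PCI results divided by tests has expectation p for any k. The percentage at a single common visit, among subjects tested, is also p in each period.

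**The case against.** The case against giving this much weight has several parts.

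- **No first-year table is planned.** SAP 5.5 and 5.6 give by-year breakdowns; SAP 5.7 does not. The 4.0/9.6/7.8% figures isolate one mechanism and do not forecast an output. This stands.
- **Testing frequency is not the only driver.** A reader might infer that the schedule alone separates the three percentages, or that etanercept must look cleaner on continuous treatment than off it. The documents do not support either reading. The active figure pools both studies over up to 10 years, and Step 3 shows that length can reverse the contrast.
- **Re-treatment need not look worse than first-course treatment.** First-course treatment began in the parent study, for which SAP 5.7 displays three visits in roughly the first year (weeks 12, 24, 48). Three draws against 4 gives 5.9% against 7.8% at p = 2%. The parent study's full laboratory schedule is not in the documents, so the true contrast is unknown.
- **Exit draws occur everywhere.** The re-treatment assessment visit includes laboratory tests, but so do the early withdrawal visits (Protocol 6.1.4). They are not counted as extra density here.
- **The impact is limited.** The study is open-label with one treatment, and no formal comparison of laboratory data between periods is planned. Entry to withdrawal is selected on inactive disease or good response (Protocol 4.1.3), so the periods would differ even on identical schedules. SAP 5.7 also reports numbers of observations by visit, from which a careful reader could see the testing density.

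These points remove any fixed direction of bias and narrow the scope. They do not make the percentages comparable: two uncontrolled features of observation pulling in different directions leave the table harder to read.

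**Conclusion.** The point holds in limited form. As planned in SAP 5.7, the crude PCI percentages for the pooled active period, withdrawal and re-treatment reflect both length of observation and first-year testing density, and cannot be compared as they stand. No net direction can be claimed in advance. At an assumed 2% per test, density alone gives about a 2.4-fold excess for withdrawal over active treatment at 12 months. Length can produce 33.2% on a full active course against 5.9% in a 6-month withdrawal.

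These sizes rest on an assumed per-test probability that is equal across periods and independent between tests. The density part applies only to abnormalities lasting less than 6 months and only to the first 12 months of withdrawal and re-treatment. The 20-draw figure counts only the parent visits that SAP 5.7 lists. Because the summaries are descriptive, the consequence is a risk of misreading a safety table, with no effect on a test or on the primary endpoint. The low cost of the remedy justifies the change.

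**What to change.** In SAP 5.7, keep the planned number (%) of subjects and footnote it, for each period, with the number of scheduled tests performed and the subject-time observed. Add one table for the active period, withdrawal set and re-treatment set, in either form:

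1. PCI results divided by scheduled laboratory tests performed, excluding repeat and unscheduled draws. The exclusion matters: Protocol 7.2 requires clinically significant abnormal values to be repeated, which would otherwise load both numerator and denominator.
2. The percentage of tested subjects with a PCI result, shown separately at each visit common to the three extension schedules (Months 6, 12, 18 and so on, counted from the start of each period). Parent-study visits go in their own columns. The visits should not be collapsed into an any-visit percentage, which would bring the length effect back.

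Restoring the Protocol 9.4.2 rate would not replace this table, for the reasons in Step 5.

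The cost is a short SAP addition and one table from data already collected, with no change to visits. In the common-visit form, results at Months 1, 3 and 9 and at unscheduled draws drop out of the new table but remain in the all-results one. Neither form removes selection into withdrawal, so a causal reading across periods stays limited, and the footnote should say so.

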5.8. Growth Parameters

Height, weight, and body mass index (BMI) will also be compared with data from standardized growth charts. Height, weight, and BMI will be summarized using Z-scores. Z-score is calculated using the following formulation:

$$Z = \frac{(X / M)^L - 1}{LS}, L \neq 0$$

Or

$$Z = \ln(X / M) / S, L = 0$$

where X is the physical measurement (eg, height, weight, BMI) and L, M, and S are the values from standardized growth charts provided by the US Centers for Disease Control website (<http://www.cdc.gov/GrowthCharts/>) by gender for children from birth to 240 months. The Z-score cannot be calculated if age > 240 months.

These summaries will be performed for FAS (active period (both parent and extension studies)), WAS and RTAS.

5.9. Efficacy Endpoints

Descriptive summary statistics will be provided for efficacy endpoints. For continuous endpoints, the summary statistics at each visit will include the number of observations, mean, standard deviation, median, minimum, maximum and 95% confidence interval for the mean. These statistics will be provided for the observed value and change from baseline. The mean percent change from baseline will be provided also. For categorical endpoints, the summary statistics will contain the frequency, percentage, and 95% confidence interval (CI) for the percentage.

These summaries will be performed for:

- FAS, active period data (both parent and extension studies. Baseline of parent study will be used for calculation of change from baseline). The reports will show the baseline (no baseline for ACRPedi responses), weeks 12, 24, 48, and 96 from the parent study and all visits from the extension study where data is collected.
- WAS. The reports will show all visits where data is collected.

- RTAS. Re-treatment period baseline will be used for calculation of change from baseline. The reports will show all visits where data is collected.

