5.4. Demography and Baseline Characteristics

Demographic, baseline characteristics (eg, subtype of JIA) and baseline disease characteristics (physician global assessment, patient/parent global assessment, Number of joints with LOM, Number of painful joints, Number of swollen joints, Pain assessment, Morning stiffness, CRP, CHAQ and HAQ. Additionally, Tender entheses score, Overall back pain VAS, Nocturnal back pain VAS, Modified Schober's test for ERA subtype; BSA of psoriasis, Physician's Global Assessment of Psoriasis for PsA subtype) data will be summarized. For continuous variables such as age, height, weight, the descriptive statistics will include the number of patients, mean, median, standard deviation, minimum, and maximum. For dichotomous variables such as sex and nominal variables such as race and ethnicity, the descriptive statistics will include the total number of patients, the count and percentage in each category. Baseline and demographic data will be summarized for subjects entered extension study (both parent study and extension study baselines), Withdrawal Analysis Set

(WAS, withdrawal period baseline), and Re-treatment Analysis Set (RTAS, retreatment period baseline).

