5.10. Health Outcomes Assessments

The CHAQ and HAQ will be summarized in the same way as the efficacy endpoints. CHAQ and HAQ results will be summarized separately.

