5.16.4. ACR Pedi Response

Scoring algorithm including missing data handling for ACR Pedi 30, 50, 70, 90, and 100: First, if any of the components have a score of zero at baseline and the post baseline score is >0, that component will be treated as worsening >30% for scoring improvement; if the baseline score is 0 and the post baseline score is also zero, improvement will be set to 0%. Then the algorithm described in the table below will be applied, based on the number of components with worsening >30%, missing, and improvement >30% (or 50% for ACR Pedi 50, etc).

Worsening>=30%	Missing	Improvement>30%	Outcome
>=2			Non-responder
1	0	>=3	Responder
		<3	Non-responder
	1	>=2	Missing
		<2	Non-responder
	2	>=1	Missing
		0	Non-responder
>=3			Missing
0	0	>=3	Responder
		<3	Non-responder
	1	>=3	Responder
		2	Missing
	>=2	<2	Non-responder

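### SAP 5.9 reports mean percent change with no rule for zero baselines; it is undefined at zero and can be dominated by a few near-zero baselines, most clearly in the withdrawal analysis set

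*SAP*

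**What the plan says.** SAP 5.9 lists the summaries: "For continuous endpoints, the summary statistics at each visit will include the number of observations, mean, standard deviation, median, minimum, maximum", plus a 95% confidence interval for the mean. It then says "These statistics will be provided for the observed value and change from baseline", and adds "The mean percent change from baseline will be provided also". The full list therefore covers the observed value and the absolute change; for percent change only a mean is named. No continuous endpoint is excepted. Section 5.10 extends the approach: "The CHAQ and HAQ will be summarized in the same way as the efficacy endpoints". Section 5 repeats every analysis in each of the three JIA subtypes.

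The baseline differs by analysis set. For the full analysis set, "Baseline of parent study will be used for calculation of change from baseline". For the re-treatment set, "Re-treatment period baseline will be used for calculation of change from baseline". For the withdrawal set (WAS), 5.9 names none; the baseline tables in 5.4 use "WAS, withdrawal period baseline".

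The one zero-baseline rule is in 5.16.4, which applies "if any of the components have a score of zero at baseline and the post baseline score is >0" and also covers zero at both times. It serves ACR Pedi responder scoring only. Section 5.16 says that missing derived endpoints are not imputed, but not what percent change is when the baseline is 0.

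**The concern.** Percent change divides by the baseline. Where the baseline is 0 there is no value, and someone must decide what to do. If such subjects are simply set to missing, the percent-change line excludes people who on these scales can only stay the same or worsen, and it no longer describes the same subjects as the absolute change next to it. With no n required for percent change, the reader might not see this.

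Where the baseline is small but not zero, the scale is lopsided: nobody can improve by more than 100%, while a worsening can be many hundreds of percent. A mean on that scale can understate a typical improvement or even take the opposite sign. At stake is whether one secondary descriptive figure can be read at face value.

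**Working it through.** The plan states no figure to reproduce, so the check is whether the statistic is defined, and how it behaves, on the plan's own scales.

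**Inputs from the documents**
- PGA: 0 to 10 on 21 circles (Protocol 7.3), so the step is 10/20 = 0.5 and zero is possible.
- CHAQ/HAQ: mean of up to eight domains scored 0 to 3 (SAP 5.16.3); the smallest non-zero score with eight domains is 1/8 = 0.125.
- WAS entry: clinically inactive disease by the Wallace definition for at least 6 months, or a good response in the investigator's judgment (Protocol 4.1.3). The definition requires no active joints and the best possible PGA (Protocol 2.2.3), which is 0.
- Anticipated enrollment: about 100 (SAP 2.2.3).

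**Zero baselines.** Percent change = 100 x (visit - baseline)/baseline. A subject who enters the WAS by the Wallace route, and still meets it at the withdrawal baseline, has baseline 0 for PGA and for active joints. If that baseline is used, the denominator is 0 and the value is undefined whatever happens later, including relapse.

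**Near-zero baselines.** One subject worsening by W% keeps the mean above zero against any number m of subjects improving by I%, as long as m x I < W.
- PGA 0.5 to 5: 100 x 4.5/0.5 = +900%. Against I = 50, m can be 17: (900 - 17 x 50)/18 = +2.8%.
- CHAQ 0.125 to 1.0: 100 x 0.875/0.125 = +700%. Against I = 50, m can be 13: (700 - 13 x 50)/14 = +3.6%.

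**Worked example (assumed values, n = 20).** Nineteen subjects go from PGA 6 to 3 (-50%) and one from 0.5 to 6 (+1,100%).
- Mean percent change: (19 x -50 + 1,100)/20 = +7.5%.
- Median percent change: -50%.
- Mean absolute change: (19 x -3 + 5.5)/20 = -2.6.
- Percent change of the means: baseline mean (19 x 6 + 0.5)/20 = 5.725, so 100 x -2.575/5.725 = -45.0%.

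**How often.** The documents give no baseline distribution and no within-subject correlation, so the following rests on assumptions. Take log-normal CRP with median 3 mg/L at baseline and 1.2 at follow-up (a 60% fall), equal log SD at both times, n = 100 and 5,000 simulated trials. The chance that the mean percent change is positive:

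| Log SD | Correlation 0.4 | 0.6 | 0.8 |
|---|---|---|---|
| 0.5 | 0 | 0 | 0 |
| 1.0 | about 2% | 0 | 0 |
| 1.2 | 33% | 1% | 0 |
| 1.6 | 97% | 61% | 0.2% |
| 2.0 | about 100% | 97% | 22% |

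The median percent change was about -60% in every cell. Even without a change of sign the mean is pulled upward: at log SD 1.0 and correlation 0.4 it was typically -28%.

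The share of subjects who worsen in this model follows directly. The log ratio has mean ln(0.4) = -0.916 and SD = log SD x sqrt(2 x (1 - correlation)). At log SD 1.6 and correlation 0.4 the SD is 1.6 x sqrt(1.2) = 1.753, so P(worse) = Phi(-0.916/1.753) = Phi(-0.523) = 0.30.

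**The case against.** The strongest reply is that little depends on this line. The primary endpoint is malignancy, efficacy is secondary, the summaries are descriptive, and no test, decision or sample size uses percent change. Section 5.9 already gives the mean, median, range and confidence interval of the absolute change, so a misleading percentage would sit beside a sound figure. In the simulation the mean absolute change was positive in at most about 1% of trials up to log SD 1.6, and in about 5% at log SD 2.0 with correlation 0.4. All of this stands and limits the weight of the point. It does not supply a zero-baseline rule.

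A reader might infer that the mean will usually have the wrong sign even when nearly all subjects improve. The documents do not support that. The 97% cell needs an assumed skew and correlation, and about 30% of subjects worsen in it. In a separate assumed model in which about 97% improve (log-normal baseline with median 8, typical improvement 60%, 5% of subjects relapsing, n = 100), the chance of a positive mean was 0, 1.3%, 17% and 36% at log SD 0.5, 1, 1.5 and 2.

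Nor should CRP stand for every endpoint: PGA and CHAQ are bounded and move in coarse steps, so their extremes are milder. In the full analysis set the parent-study baseline applies, and the parent study's entry criteria are not in these documents, so zeros there may be rare or common. The SAP also does not say that zero-baseline subjects are dropped; the defect is that it says nothing. Finally, the available text of Protocol 9.2.2 breaks off before it could show any matching wording.

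**Conclusion.** The point holds as a minor defect of specification. Two parts need no distributional assumption: percent change is undefined at a zero baseline and 5.9 has no rule for it, and on the plan's own scales a single near-zero baseline can outweigh more than a dozen subjects who improve by half.

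The WAS is the clearest case, on condition that the withdrawal baseline is the one used and that the subject entered by the Wallace route. Subjects admitted on the investigator's judgment need not have zeros.

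The frequency of distortion or a reversed sign elsewhere cannot be stated from the documents. The assumed range is 0 to about 100%: negligible with tight baselines, large with strongly skewed and weakly correlated ones. The absolute-change results are not affected.

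**What to change.** In SAP 5.9, replace the mean percent change with one of these:
- the median percent change with quartiles, the n with baseline above 0, and the number with baseline 0 together with their absolute change; or
- 100 x (mean at visit - mean at baseline)/mean at baseline, in subjects with both values.

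For the WAS, state which baseline applies and rely on absolute change for PGA and active joints. Section 5.10 follows automatically, since it refers to the efficacy summaries.

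The cost is a sentence or two in the SAP and a small change to table programming. No new data or visits are needed, and the absolute-change tables stay as they are.
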